Engaging Working Memory and Distress Tolerance to Aid Smoking Cessation
NCT03565497
R21 DA046963

Updated: 8/5/2019

PROTOCOL

Design Overview

This study is designed to evaluate the success of mechanistic target engagement in two specific contexts: under standard smoking conditions and under nicotine deprivation (stress) conditions. After screening, consent, and baseline assessment, participants selected on the basis of inclusion/exclusion criteria will be randomized to one of three intervention conditions: (1) a health-education control condition (CC), (2) a mindfulness training condition (MT), or (3) a mindfulness training condition combined with training applying mindfulness skills in the context of interoceptive exposure (Mindfulness+IE). Following 6 sessions of these interventions, delivered over 3 weeks, participants will then undergo the standard smoking assessment of mechanistic targets. Two days later (and matching the progression to quit-attempt challenges following treatment), participants will undergo the deprivation window assessment (14 hours of smoking abstinence) of these same mechanistic targets, followed by evaluation of lapse behavior and smoking topography in the McKee paradigm to yield: (1) latency to initiate smoking during a monetarily reinforced delay period, (2) the number of cigarettes smoked during a subsequent 60-minute self-administration period, and (3) exploratory analysis of smoking topography: puff volume, puff duration, and inter-puff interval. Participants will be recruited to Boston University through study advertisements targeted to low SES neighborhoods, with attention to health service centers and religious institutions serving low SES individuals. Investigators will work closely together to ensure the scientific integrity (rigor and reproducibility) of the project and data analyses.

Participant Selection

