Following telephone screening for basic eligibility, participants will be scheduled for an informed consent interview and subsequent baseline assessment session. Interventions are to be completed over the subsequent 3 weeks, and post-treatment assessments of the mechanistic targets are scheduled for one-week (standard smoking assessment) and one week + 2 days (deprivation-window assessment) from the last intervention session. For the standard smoking window assessments, participants are asked to smoke .5 hour before the scheduled assessment session. The deprivation-window assessment is scheduled two days later, (for example, scheduled for 12:00 noon, with smoking to cease at 10PM the night before). Upon arrival to the lab, nicotine abstinence will be verified by expired CO levels, as determined by a cut-off of half of the participant's screening session CO concentration or <10 PPM (those failing will be rescheduled). After verification of abstinence, participants will complete assessment of the triple-risk mechanistic target variables. These assessments will be followed by the McKee Lapse protocol ([name], *Study Consultant*, will train the study team and help monitor quality in these procedures): participants will be instructed that over the next 50 min, they will have the option to initiate a cigarette self-administration (smoking) session at any point or to delay initiation in exchange for monetary reinforcement. If participants choose to delay, they will be awarded funds for each 5-minute increment they are able to resist smoking. Once participants choose to end the delay period in order to smoke (or resist smoking for the entire 50 minute delay period), they will then participate in a 60-minute cigarette self-administration session, in which they will be given the choice to either smoke their

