Engaging Working Memory and Distress Tolerance to Aid Smoking Cessation

NCT03565497

R21 DA046963

Updated: 8/5/2019

Analytic Plan

Note: Due to limited sample size the full analytic plan for this project could not be enacted validly.

Analyses for outliers, non-normal distributions, nonlinear relations, and influence statistics will be conducted; data transformations will be considered where appropriate. We will analyze data using mixed effects regression models (MRM) because they allow inclusion of all participants regardless of missing data (which improves power and generalizability) and are the recommended method for longitudinal data analysis (Hamer & Simpson, 2009). For each analysis, the distribution of the DVs will be evaluated and appropriate linking functions and outcome distributions will be used if the DVs are not normally distributed (in these cases the analysis will be generalized linear mixed models). For all analyses, the following baseline assessments will be included as covariates in the analyses: cigarette use in the last 30 days, FTCD score, QSU score, BRIEF-A scores for the Behavioral Regulation Index, and psychological distress from the K6+ symptoms.

Aim 1. We will perform repeated-measures MANCOVAs using MRMs. IVs will be intervention condition (3 levels) and assessment context (smoking vs. deprivation; 2 levels). One MANCOVA will be performed for each of the three risk categories (stress reactivity, WMC, DT) with the multiple measures of each risk factor being the multivariate DVs. For Aim 1a, we will use contrasts to test whether Mindfulness and Mindfulness+IE will each significantly improve stress reactivity, WMC, and DT relative to the control condition (CC), during the standard smoking assessment. For Aim 1b, we hypothesize that Mindfulness+IE will significantly improve stress reactivity, WMC, and DT relative to both the Mindfulness and CC conditions, during the smoking deprivation assessment.

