Aim 2: For Aim 2, we will examine the bivariate associations between the triple risk variables and McLee Lapse outcomes. We will attempt to balance the need to determine which individual variables at which assessment context are related to which outcomes, with the need to minimize the number of tests. Thus, multivariate MRM (MMRM) will be used with the 2 McLee Lapse outcomes as the multiple DVs. One MMRM will be performed for each individual risk variable, with the IVs in each MMRM being the 2 assessments (smoking context and deprivation context) of the individual risk variable. This MMRM will be compared to the same MMRM that constrains the coefficients of each IV to be equal. If the likelihood ratio test indicates that the constrained model does not fit the data worse than the unconstrained model, then the relation between the risk factor and the outcomes does not differ by assessment context. If the test is significant, assessment context would be considered a moderator of the relation between the risk factor and outcome. Further, we will include a dummy variable to differentiate the 2 outcomes (0=latency, 1=number of offers of cigarettes resisted). If an interaction between that dummy variable and an IV regression coefficient is significant, the relation between the risk factor and outcome is different for the 2 outcomes.

Aim 3: To determine which of the individual risk assays are related to outcomes over and above the other factors, including consideration of the assessment context of each risk factor, we will perform analyses similar to the MMRM in Aim 2 with the following differences: 1) if Aim 2 shows that the relation between a risk assay and outcomes did not differ by context, the 2 measures of the risk factor will be averaged across the 2 contexts and used as a single predictor, and 2) all the risk factors will be entered as simultaneous predictors of outcomes. Non-significant predictors will be dropped and the analysis rerun.

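### Latency to smoke is right-censored at 50 minutes, but the SAP names no method for Aims 2 and 3 that treats 50 as at least 50

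*SAP*

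**What the plan says.** Protocol, Procedures and the McKee Protocol: "participants will be instructed that over the next 50 min, they will have the option to initiate a cigarette self-administration (smoking) session at any point". The delay ends when the participant chooses to smoke, or when they "resist smoking for the entire 50 minute delay period". Payment accrues for each 5-minute increment resisted, so the window holds 50 / 5 = 10 increments.

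Protocol, Design Overview, defines the two main lapse outcomes as "latency to initiate smoking during a monetarily reinforced delay period" and "the number of cigarettes smoked during a subsequent 60-minute self-administration period".

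SAP, Aim 2: "multivariate MRM (MMRM) will be used with the 2 McLee Lapse outcomes as the multiple DVs", with one model per risk variable. An outcome indicator is added, coded 0 for latency and 1 for cigarette offers resisted. A significant interaction between it and a risk variable is read as a different relation for the two outcomes. Aim 3 uses a similar model with all risk variables together and drops non-significant predictors.

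SAP, Analytic Plan, has a general provision: transformations will be considered, and "appropriate linking functions and outcome distributions will be used if the DVs are not normally distributed", giving generalized linear mixed models. Neither document mentions censoring, a Tobit model or a time-to-event model.

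**The concern.** A value of 50 for someone who never smoked in the delay period is a lower bound. None of the SAP's tools for non-normal outcomes uses that fact. A transformation moves the cap to another number, and an ordinary generalized linear mixed model still takes the capped value as exact.

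Three results could be affected: the size of the latency slopes in Aim 2; the choice of which risk assays survive in Aim 3, because retention depends on significance; and the Aim 2 test of whether a risk variable relates differently to the two outcomes, because a cap on only one of them can create a difference in slopes.

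**Working it through.** **The plan's own figure.** The documents give no ceiling share and no latency slope. The nearest figure is in the Power Analysis: more than .80 power at d = .39 for Aim 2 with N = 75. The software inputs are not given, so it cannot be rerun. At two-sided 5% (assumed), reading d as a median-split difference gives power .39. Reading .39 as a standardised slope gives Φ(atanh(.39) × √72 − 1.96) = Φ(1.53) = .94. The figure is neither confirmed nor refuted, and nothing below depends on it.

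**Inputs.** From the documents: cap at 50 minutes, N = 75. Assumed: latent (log) latency normal, true standardised slope b = .35, share p at the cap of 20%, 40% or 60%.

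**Raw slope.** For a normal predictor x and latent latency y, Cov(x, min(y, c)) = b × P(y < c) = b(1 − p). This gives .35 × .8 = .28, .35 × .6 = .21 and .35 × .4 = .14.

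**Standardised association.** Divide the raw slope by the SD of the capped outcome. With c the (1 − p) normal quantile and φ the normal density, the mean is −φ(c) + cp and the mean square is (1 − p) − cφ(c) + c²p. At p = .4, c = .253 and φ(c) = .386. The mean is −.285, the mean square .528, the variance .528 − .081 = .447 and the SD .668. The retained fraction is .6 / .668 = .90. The same steps give .96 at 20% and .81 at 60%. The losses are therefore 4%, 10% and 19%, much smaller than for the raw slope, because the cap also shrinks the outcome's variance.

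**Simulation at N = 75, b = .35** (linear fit to capped log latency against a right-censored normal fit):

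| Share at 50 minutes (assumed) | 20% | 40% | 60% |
|---|---|---|---|
| Raw slope, linear | .28 | .21 | .14 |
| Raw slope, censored | about .35 | about .35 | about .36 |
| Observed standardised association | .33 | .32 | .29 |
| Power, linear | 87% | 81% | 74% |
| Power, censored | 88% | 86% | 80% |

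The power gaps are 1, 5 and 6 points. A separate run of 1,000 trials gave 84%, 80% and 72% against 87%, 83% and 78%, so gaps of 3, 3 and 6. With a true slope of zero, the linear test rejected close to 5% of the time and the censored test 5% to 6%.

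**Part of the loss cannot be recovered.** At b = .33, power on the capped outcome is .80, .73 and .64, against .83 with no cap. A censored model wins back only some of that; the rest is information the 50-minute window never collects.

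**Comparison of the two outcomes.** Equal latent slopes of .33, residual correlation .5, nominal 5%, 4,000 trials per scenario:

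| Setting | 20% | 40% | 60% |
|---|---|---|---|
| Only latency capped, common latent scale | .09 | .25 | .48 |
| Only latency capped, both standardised after capping | .04 | .05 | .08 |
| Both capped equally | .04 | .05 | .06 |

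With no cap at all, but raw units left as they are (assumed SDs of 18 minutes and 1.2 units), false rejection is already .80.

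**The case against.** The strongest reply is that the SAP leaves the final model open. It promises to examine each outcome's distribution and to choose a suitable one. That stands to this extent: the gap is an omission, not a stated choice of an uncensored normal model. A reader might infer that stacking the outcomes forces one family on both. The text does not say so, and a multivariate generalized linear mixed model can give each outcome its own family. What remains is that no tool the SAP names handles a lower bound.

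Second, the target may be minutes resisted within the paid window. For that quantity 50 is an exact value and there is no attenuation, only a question of linearity and variance. This is a legitimate target, but the SAP does not state it. The slope losses above are relative to latency beyond the window.

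Third, a reader might take the fall of the raw slope by 20% to 60% as the damage to the tests. It is not. Aim 3 retains predictors by significance, which follows the standardised association and the power, and those move far less.

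Fourth, a reader might conclude that the cap invalidates the between-outcome test. The second table does not support that: the distortion nearly vanishes when the outcomes are standardised or similarly bounded, and mixing minutes with a count is the larger threat. Offers resisted may itself be bounded.

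Finally, the SAP notes that its full plan could not validly be carried out at the sample size reached. That limits what can be run, but the point applies to any analysis of latency that is reported.

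**Conclusion.** The point holds as an omission with a conditional cost. Latency is right-censored by design and no named method respects that. If 20% to 60% reach 50 minutes, the raw slope keeps about 80% to 40% of its latent value, the standardised association loses roughly 5% to 20%, and power is about 1 to 6 points lower than with a censored model. If few reach the cap, little is lost. The documents do not support saying that the slopes are in fact attenuated by a given amount, or that the single-outcome tests give excess false positives.

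The comparison of the two outcomes can be distorted, but only when latency alone is capped and no common scale is set. The SAP states no such scale.

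These sizes rest on normal latent (log) latency, slopes of .33 to .35, N = 75 and the assumed ceiling shares. Amending the SAP is worthwhile because the remedy is cheap and the ceiling share was unknown when the plan was written.

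**What to change.** 1. Analyse latency as right-censored at 50 minutes, with the same predictors and baseline covariates. A Tobit or accelerated-failure-time model would serve, as would a discrete-time hazard model on the ten 5-minute increments. If the intended target is minutes resisted within the window, say so and give the censored model as a sensitivity analysis.
2. Report the share reaching 50 minutes.
3. Keep the planned comparison of the two outcomes. Use a joint model with a censored latency component, and state the common scale on which the slopes are compared. Define the second outcome and its direction in the same place: the Protocol counts cigarettes smoked, whereas the SAP's indicator codes offers resisted, which runs the opposite way. State whether it is bounded.

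The cost is SAP wording and slightly more complex modelling, plus a distributional or hazard assumption for latency. Few events would strain the censored model: at 60% capped, 75 × .4 = 30 participants smoke in the window, against seven predictors in each Aim 2 model (five baseline covariates and two assessments of the risk variable). In a discrete-time model, a simple time trend would then be safer than ten separate interval terms. Fitting wholly separate models and reporting the effects side by side would be simpler, but it would abandon a question the SAP set out to test.

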We anticipate consenting and randomizing up to 107 participants in order to reach an assessed sample (defined as providing post-treatment assessments, including the McKee protocol) of 75, low SES, male and female smokers (ages 18-65). For inclusion in the study, participants must (1) be between 18 and 65 years of age; (2) have reported household income of less than \$30,000 per year; (3) be a regular smoker for at least one year; (4) report daily smoking (minimum of 5 cigarettes per day and biochemically confirmed via Carbon Monoxide [CO] analysis; > .10 ppm CO); and (5) and not be presently engaged in a quit attempt. Exclusion criteria include history of psychosis as determined by a brief psychotic screen, pregnancy, nursing mothers, medical conditions that would contraindicate smoking (e.g., current diagnoses of chronic medical diseases including heart disease, chronic obstructive pulmonary disease, or seizure disorders - assessed during telephone prescreen and initial assessment via medical checklist), nicotine use other than cigarette smoking, current use of any pharmacotherapy for smoking cessation, or insufficient command of the English language (i.e., cannot carry on a conversation with an interviewer in the English language or read associated text).

Feasibility and Participant Compensation

The study team and consultants have a rich publication history reflecting collaboration on studies of health behaviors, distress intolerance, and, specifically smoking characteristics and treatment outcome.^{1,73,76,90-93} [name] at Boston University has a history of successfully attracting smokers for psychopathology studies, easily completing 100 screens per year. Moreover, [name] is directing mindfulness interventions to low SES adolescents recruited to his ongoing study, R21DA041531. Recruitment/adherence is aided in the current study by financial compensation for all assessments and intervention sessions, with compensation of up to \$180 per participant, depending on McKee Lapse paradigm results.

Procedures and the McKee Protocol

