Exploratory Analyses: 1) In consideration of sex as a biological variable, sex and the interactions between sex and all predictors will be considered in exploratory analyses for each Aim. 2) We will examine whether ASI moderates the effects of treatment condition and context (stress) on the risk categories in Aim 1, by adding ASI and its interaction with the treatment condition and context to the MMRMs in Aim 1. 3) We will examine smoking topography as a predictor of outcomes in Aims 2 and 3. 4) We will examine number of intervention sessions attended and dropouts to aid data interpretation and future study planning.

Power Analysis. We used PinT 2.12 (Power in Two-Level models) to calculate the smallest effect size detectable given our N=75 at the deprivation assessment. Since no power analysis programs are available for multivariate MRM, we performed power analyses for the univariate MRMs knowing that power for the multivariate MRMs will be greater.¹⁰⁸ PinT indicated that we had greater than .80 power to detect an effect size of $d = .40$ for **Aim 1**, $d = .39$ for **Aim 2**, and $d = .48$ for **Aim 3**. As per research detailed above,^{54,63,64,71,82,109} there is preliminary evidence indicating that our interventions have the ability to activate mechanistic targets, and for mechanistic targets to be related to clinical outcomes, at effect sizes beyond these powered values.

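### SAP Aim 2 reads a non-significant likelihood-ratio test as proof that assessment context makes no difference, and a significant one as moderation by context; neither conclusion follows

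*SAP*

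**What the plan says.** SAP, Aim 2, fits one multivariate mixed model per risk variable. The two lapse outcomes are the dependent variables and the two assessments of that risk variable are the predictors; the SAP's opening paragraph adds five baseline covariates. A likelihood-ratio test compares this model with one that constrains the two coefficients to be equal. Both results are given a firm reading:

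- Not significant: "then the relation between the risk factor and the outcomes does not differ by assessment context".
- Significant: "assessment context would be considered a moderator of the relation between the risk factor and outcome".

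SAP, Aim 3, carries the first reading forward. Where Aim 2 found no difference, "the 2 measures of the risk factor will be averaged across the 2 contexts and used as a single predictor".

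The SAP's Power Analysis gives more than .80 power for d = .39 in Aim 2, "given our N=75 at the deprivation assessment". It describes the basis in these words: "we performed power analyses for the univariate MRMs knowing that power for the multivariate MRMs will be greater". It does not say that d = .39 refers to a difference between two coefficients.

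The Protocol (Design Overview; Procedures and the McKee Protocol) places the standard smoking assessment one week after the last session and the deprivation assessment two days after that, for every participant. The lapse test follows the deprivation measures in the same visit. No counterbalancing is described.

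**The concern.** Failure to reject equality is not evidence of equality. To support a claim that two coefficients are the same, the plan needs a margin fixed in advance and an interval that lies inside it. The SAP has neither.

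This matters because whether a risk factor acts differently under deprivation is one of Aim 2's own questions, and the Design Overview builds the study around the two contexts. The result also decides how each variable enters Aim 3, so a test that missed a real difference would remove the distinction from the later model.

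The significant branch has a separate fault. Context is completely tied to visit order and to closeness to the outcome. A predictor measured minutes before the lapse test may relate to it more strongly than one measured two days earlier, whatever deprivation does.

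**Working it through.** **The plan's own figure.** The inputs to the power program are not given, so d = .39 can be neither reproduced nor refuted. Converted to a correlation, r = .39/√(.39² + 4) = .191. Fisher's z with n = 75 then gives atanh(.191) × √72 = 1.64, which is about 38% power two-sided. Read directly as a correlation or slope of .39, power is about 92% to 94%, compatible with the claim. Neither reading is power to detect a difference between two coefficients.

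**Inputs for the equality test.**

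- From the documents: N = 75, two outcomes, two predictors, five covariates. Residual degrees of freedom are 75 − 8 = 67.
- Assumed: alpha .05; standardised scales; deprivation slope b and smoking-context slope 0, the same for both outcomes; correlation between visits ρ; residual correlation between outcomes r_y of .3 to .7. The SAP does not say whether the constraint is tested on 1 or 2 degrees of freedom, so both are shown.

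**Formula.** SE(difference) = √[(1 − b²)(1 + r_y) / (67(1 − ρ))]. The noncentrality is λ = b²/SE², and power comes from the noncentral chi-square distribution. In each row below, the low figure is r_y = .7 with 2 df and the high figure is r_y = .3 with 1 df.

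| Slope b | ρ | λ | Power |
|---|---|---|---|
| .30 | .3 | 2.73 to 3.57 | 30% to 47% |
| .30 | .5 | 1.95 to 2.55 | 22% to 36% |
| .30 | .7 | 1.17 to 1.53 | 15% to 24% |
| .30 | .8 | 0.78 to 1.02 | 11% to 17% |
| .40 | .3 | 5.25 to 6.87 | 52% to 75% |
| .40 | .5 | 3.75 to 4.91 | 39% to 60% |
| .40 | .7 | 2.25 to 2.95 | 25% to 40% |
| .40 | .8 | 1.50 to 1.96 | 18% to 29% |

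Worked example, b = .30, ρ = .5, r_y = .3: SE = √(.91 × 1.3/33.5) = .188; λ = .09/.0353 = 2.55; power is 36% on 1 df.

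**Simulation check.** A simulated two-outcome test (n = 75, five covariates, 2 df, r_y = .4, 4,000 runs) rejected in 29% of runs at ρ = .6 and 23% at ρ = .7 for a true difference of .30. For a difference of .39 it rejected in 42% and 34%. These are somewhat above the formula (22% and 17% for .30, taking residual variance .9). Part of the gap is that the simulated test rejected 6.6% of the time under true equality.

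**Precision.** For b = .30 the 95% CI half-width, 1.96 × SE, runs from about .31 (ρ = .3, r_y = .3) to .67 (ρ = .8, r_y = .7). Equality could be supported only against margins wider than that.

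**The significant branch.** Suppose deprivation has no effect. Each score is a lasting trait (variance .5), a state on that day (.3) and error (.2), so ρ = .5. The outcome depends on the trait and on the state on the day of the lapse test. If the second score correlates .40 with the outcome, the first correlates .40 × .5/.8 = .25. The difference between the two regression coefficients is (.40 − .25)/(1 − .5) = .30. Correlations of .30 and .50 give differences of .225 and .375. The simulated test rejected in 23%, 32% and 44% of runs for .30, .40 and .50. The variance split is illustrative: with trait .6 and state .2 the three differences become .19, .25 and .31; with .4 and .4 they become .25, .33 and .42.

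**The case against.** Five points can be made for the plan.

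**Two outcomes are modelled jointly.** This raises power above a one-outcome test, which for a slope of .30 has 27%, 18% and 14% at ρ = .5, .7 and .8. The point stands, and the table uses the two-outcome model for that reason. A reader might still infer that the rule would usually miss a difference whatever the inputs. The documents give no correlation or expected slope, and at b = .40 with ρ = .3 the test finds the difference more often than not.

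**Wrong averaging costs little in Aim 3.** If only the deprivation score predicts with r = .30, the average correlates .30 × √((1 + ρ)/2) with the outcome, which is .26, .28 and .285 at ρ = .5, .7 and .8. That is a loss of 5% to 13%. This stands; the main harm is the false statement about context.

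**The visit order is deliberate.** The Design Overview says it mirrors the approach to a quit attempt. That justifies the schedule, and the order should not be read as a design error. It does not separate context from timing.

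**Practice effects.** A reader might infer that repeated testing alone explains a difference. A uniform practice gain shifts means and leaves slopes unchanged; it matters only if it alters spread, reliability or rank order. Same-session proximity is the stronger mechanism.

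**The SAP's opening note.** It says that the full plan could not be carried out validly with the sample obtained. A reader might infer that false context conclusions were in fact drawn. The note does not say which analyses were dropped, so the documents do not show this; nor does the note withdraw the rule. A sample below 75 would lower power further.

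**Conclusion.** The rule is wrong as written in its non-significant branch, and missing a caveat in its significant one. For a slope of .30, a real difference would be declared absent in about 64% to 89% of studies when the visits correlate .5 to .8, and in at least about 53% when they correlate .3. For a slope of .40 the corresponding figures are about 40% to 82%, and at least about 25%. They rest on the planned 75 assessed participants, alpha .05, equal effects on both outcomes and the assumed correlations.

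A significant test shows that the two assessments relate differently to the lapse outcomes. It does not show that deprivation is the reason. The proximity simulation shows that such a result can arise without any deprivation effect; it does not show that it would in this trial.

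The wider inference that the SAP's d = .39 is itself mistaken is not supported, because its inputs are not stated.

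**What to change.** Change the SAP text as follows.

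1. For each risk variable, report the difference between the two context coefficients with a 95% CI.
2. Describe a non-significant test as inconclusive, and remove the statement that the relation does not differ.
3. Choose the form in which each risk variable enters Aim 3 in advance, so that it does not depend on this test. The choice is the sponsor's. Averaging every assay would be simple but would sit badly with Aim 3's stated interest in context; keeping both measures preserves context but adds predictors.
4. Describe a significant result as a difference between the two assessments, with context, order and proximity to the lapse test combined.

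No new data or procedures are needed. Items 1, 2 and 4 concern reporting and wording; item 3 alters how the Aim 3 model is specified. The price is fewer definite statements about context.

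### SAP Aim 2 reads an outcome-by-risk-factor interaction as a different relation for latency and the count, but sets no common scale for the two outcomes

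*SAP*

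**What the plan says.** SAP Aim 2 fits one multivariate mixed model per risk variable, "with the IVs in each MMRM being the 2 assessments (smoking context and deprivation context) of the individual risk variable". The two lapse outcomes are the joint dependent variables, and the SAP adds: "Further, we will include a dummy variable to differentiate the 2 outcomes (0=latency, 1=number of offers of cigarettes resisted". It then fixes the interpretation: "If an interaction between that dummy variable and an IV regression coefficient is significant, the relation between the risk factor and outcome is different". The comparison meant is that between latency and the count.

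Three general statements in the SAP's Analytic Plan bear on this:

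- On scale: "data transformations will be considered where appropriate".
- On distribution: "appropriate linking functions and outcome distributions will be used if the DVs are not normally distributed".
- On adjustment: "For all analyses, the following baseline assessments will be included as covariates in the analyses". Five covariates are listed. Nothing says whether their effects may differ between the two outcomes.

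The Protocol (Procedures and the McKee Protocol) describes latency over a 50-minute window paid in 5-minute increments, so either unit would be natural. The Protocol (Design Overview) defines the count as cigarettes smoked, whereas SAP Aim 2 uses offers resisted.

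**The concern.** A slope in minutes per unit of risk variable and a slope in cigarettes per unit of risk variable are not comparable quantities. In a linear model on raw units, the dummy-by-risk-variable interaction tests whether those two numbers are equal. They will differ for any risk variable that predicts both outcomes equally well, unless the outcomes have equal SDs. The stated reading therefore does not follow from the test.

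Two errors are possible. A working-memory or distress-tolerance measure may be said to act differently on delay and on later smoking only because minutes are numerically larger than cigarettes. Or a measure that relates only to the count may go unnoticed because variation in latency swamps it. The provisions on transformation and link functions do not settle this, because they concern distributional shape and not comparability of the two coefficients.

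**Working it through.** **The plan's own figure.** The only number given for Aim 2 is d = .39 at better than .80 power with N=75 (SAP, Power Analysis). It comes from univariate models, and the PinT inputs are not given. Read as a two-group d with 37.5 per half, it gives two-sided power of .39; read as a correlation, it gives .94. It can be neither confirmed nor refuted, and nothing below depends on it.

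**Inputs.** From the documents: N=75, two assessments of each risk variable, five covariates, a 50-minute cap and 5-minute increments. Assumed, because the documents give no values:

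- outcome SDs of 18 (minutes) v 1.5 (count), or 3.6 (5-minute units) v 2;
- correlation r=.6 between the two assessments, and residual correlation ρ=.3 between the outcomes;
- each covariate correlated .2 with the risk variable;
- a two-sided 5% test.

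**Raw slopes.** With the risk variable in SD units, raw slope = standardised slope × outcome SD. For a standardised slope of .3 on both outcomes:

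- Minutes: .3×18 = 5.40 v .3×1.5 = 0.45, difference 4.95.
- 5-minute units: .3×3.6 = 1.08 v .3×2 = 0.60, difference 0.48.
- z-scored: .3 v .3, difference 0.

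**Hand approximation, ignoring covariates.** The variance of the within-person outcome difference is (1−β²)(s₁²+s₂²−2ρs₁s₂), and SE = σ/√[N(1−r²)], where √(75×.64) = 6.93.

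- Minutes: .91×(324+2.25−16.2) = 282, σ = 16.8, SE = 2.42. 4.95/2.42 = 2.04, so about 53% significant.
- 5-minute units: .91×(12.96+4−4.32) = 11.5, σ = 3.39, SE = 0.49. 0.48/0.49 = 0.98, so about 17%.

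**Simulation with the five covariates, each with its own effect on each outcome** (4,000 replicates per cell; percentage significant):

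| Case | Minutes, 18 v 1.5 | 5-minute, 3.6 v 2 | z-scored |
|---|---|---|---|
| Equal slopes .3, N=75 | 45 | 14 | 4 |
| Equal slopes .3, N=50 | 32 | 11 | 5 |
| Equal slopes .3, N=30 | 18 | 8 | 4 |
| Real difference (0 latency, .5 count), N=75 | 6 | 43 | 81 |

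Changing only the latency unit, with the count SD held at 1.5, moves the rate from 45% to 23%. Only the SD ratio matters: ratios of 1, 2, 5 and 12 give 5%, 17%, 37% and 46%. A random-intercept mixed model with common covariate slopes (300 replicates) gives 53%, 18% and 5% for the three columns of the first row.

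**Bounded outcomes.** With latency capped so that 20-60% reach 50 minutes, the count bounded at 4 or 8, and slopes of .3, raw minutes give 26-42% and z-scored outcomes 4-5%. The real difference is found 5-8% of the time in raw minutes and 68-78% z-scored.

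**No association with either outcome.** If covariate effects may differ by outcome, the test holds 5%. If covariate slopes are common, it need not. With covariates predicting both outcomes at .2, each leaves a difference of .2×18 − .2×1.5 = 3.30 raw units that a common slope cannot absorb, and the interaction is significant about 13% of the time in raw minutes. z-scoring alone does not cure this in general: with covariates predicting latency only, the z-scored test with common slopes rejects about 11%, against about 5% with outcome-specific covariate terms.

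**The case against.** The strongest reply is that the SAP never commits to raw units or an identity link. It requires each distribution to be evaluated, and a capped latency and a small count may well lead to generalised models. Under a log link the latency unit affects only the intercept, so the unit problem disappears. This stands, and the 45% figure belongs to the raw-unit linear case alone. What remains is that the scale of comparison is still unstated. In a log-link side check against equal standardised association, rejection was 5% with equal coefficients of variation and 13-23% when they differed roughly two- to threefold.

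The raw test is also a valid test of equal raw slopes. That is true; the fault lies in reading it as a different relation.

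Finally, the consequence is limited. The test feeds no later step, and the SAP states: "Due to limited sample size the full analytic plan for this project could not be enacted validly". That lowers the importance of the point. The note does not say which parts were dropped, and it supplies no scale.

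A reader might infer more than the documents support:

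- *That reported Aim 2 results are wrong.* The documents do not show which model or unit was used, or whether this test was run.
- *That Aim 3 is contaminated.* Its averaging depends on the likelihood-ratio test of context, which is a separate comparison. Aim 3 carries over the dummy only by implication ("we will perform analyses similar to the MMRM in Aim 2 with the following differences") and was not simulated.
- *That the outcomes point in opposite directions.* Under the SAP's coding, higher values of both mean more resistance. The Protocol's definition of the count would reverse one of them, so the wording needs reconciling, but the point does not rest on it.

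**Conclusion.** The point holds as a minor one. The SAP's reading of the interaction needs a common scale that it does not supply. That raw slopes depend on outcome SDs is algebra; the size of the effect depends on assumptions. At N=75 with equal standardised slopes of .3, the raw-unit linear test is significant in 41-47% of trials in minutes (SDs 15-20 v 1-2) and 10-34% in 5-minute units (3-4 v 1-2), against 4-5% z-scored. The rates also depend on the model: with one risk measure and no covariates they are 28% at an SD ratio of 2 and 69% at a ratio of 10. The direction is therefore firmer than any single figure.

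It would be too strong to say that the test has an inflated error rate in general. With no association and outcome-specific covariate effects it holds 5%; with equal SDs and equal standardised slopes it rejects 5-6%. It would be equally wrong to say that a null association always protects it, given the result for common covariate slopes.

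**What to change.** For the between-outcome comparison in Aim 2, and in Aim 3 if the dummy is kept there, state that:

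1. Both outcomes are scored so that higher means more resistance, and z-scored before stacking.
2. Outcome-by-covariate terms are included for all five baseline covariates.
3. Residual variances are outcome-specific, and standard errors are robust or bootstrapped.
4. The interaction is interpreted only as a difference in standardised association.
5. A count or other non-normal model chosen under the distribution rule is not used for this interaction test.

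Use one definition of the count in both documents.

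The cost is SAP wording and a few lines of code, with no new data. Slopes for this comparison are in SD units rather than minutes or cigarettes. A Gaussian working model is applied to bounded outcomes. The covariate terms use five degrees of freedom, and robust errors cost about 3-6 percentage points of power in the bounded-outcome check. If the distribution rule leads to a generalised model, the z-scored comparison is one additional model, which sits a little uneasily with Aim 2's wish to limit the number of tests.
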